4.2.3.3. Death

Death information are taken on 'Adverse Event' (serious criteria for immediate reporting = Death) and 'Post withdrawal follow-up (Patient status = Death) e-CRF pages.

In case of death reported on 'Adverse Event' page, the date of death is compared to the date of last intake + (*) days to classify occurrence on treatment or during follow-up.

(*): 30 days for regimen QW.

4.2.3.4. Clinical laboratory evaluation**Values**

Only reliable values are considered for analyses. Unreliable values are flagged into the database.

WBC differentiation, including values of neutrophils, basophils, eosinophils, monocytes, lymphocytes and blasts, will be ignored if blast value is missing/not done or the differentiation is automated, as considered not reliable.

In case of **multiple samples**:

- Each post-baseline value (test, re-test, planned, unplanned) measured under treatment is taken into account for analyses.

Units

All parameters will be analysed in international units (IU).

Abnormal values

Abnormal values are described according to:

- Reference laboratory ranges for the non-gradable parameters.
- NCI-CTCAE version 5.0 grade for gradable parameters.

Laboratory reference limits and NCI-CTCAE version 5.0 grades are reported in the database.

For the parameters which are gradable according to CTCAE v5.0, the grades will be derived using the local laboratory reference limits in analysis datasets.

Table (4.2) 4 - Definition of CTCAE grade - Version 5.0 - Gradable parameters

Parameter	Grade 1	Grade 2	Grade 3	Grade 4
Sodium (mmol/l) – Hypernatremia]ULN;150]]150;155]]155;160]	>160
Sodium (mmol/l) - Hyponatremia	[130;LLN[-	[120;130[< 120
Potassium (mmol/l) – Hyperkalemia]ULN;5.5]]5.5;6]]6;7]	> 7
Potassium (mmol/l) – Hypokalemia		[3.0;LLN[[2.5;3.0[< 2.5
Amylase (IU/L) - High	>ULN – 1.5 x ULN	>1.5 x ULN – 2 x ULN	>2 x ULN – 5 x ULN	> 5 x ULN
Triacylglycerol Lipase (IU/L) - High	>ULN – 1.5 x ULN	>1.5 x ULN – 2 x ULN	>2 x ULN – 5 x ULN	> 5 x ULN
Ionized calcium (mmol/l) - High]ULN;1.5]]1.5;1.6]]1.6;1.8]	> 1.8
Ionized calcium (mmol/l) - Low	[1.0;LLN[[0.9;1.0[[0.8;0.9[< 0.8
Magnesium (mmol/l) - Hypermagnesemia]ULN;1.23]	-]1.23;3.30]	> 3.30
Magnesium (mmol/l) - Hypomagnesemia	[0.5;LLN[[0.4;0.5[[0.3;0.4[< 0.3
Albumin (g/l) - Low	[30; LLN[[20; 30[< 20	-
Glucose (mmol/l) - Hypoglycemia	[3.0;LLN[[2.2;3.0[[1.7;2.2[< 1.7
Total cholesterol (mmol/l) - High]ULN;7.75]]7.75;10.34]]10.34;12.92]	> 12.92
Triglycerides (mmol/l) - High	[1.71;3.42]]3.42;5.7]]5.7;11.4]	> 11.4
Serum creatinine increased (umol/L)	>ULN – 1.5 x ULN	>1.5 x baseline – 3.0 x baseline (if baseline available) OR >1.5 x ULN – 3.0 x ULN	>3.0 x baseline (if baseline available) OR >3.0 x ULN – 6.0 x ULN	>6.0 x ULN
Total bilirubin increased (umol/L)	>ULN – 1.5 x ULN if baseline is normal [≤ULN]; 1.0 x baseline – 1.5 x baseline if baseline is abnormal [>ULN]	>1.5 x ULN – 3.0 x ULN if baseline is normal [≤ULN]; >1.5 x baseline – 3.0 x baseline if baseline is abnormal [>ULN]	>3.0 x ULN – 10.0 x ULN if baseline is normal [≤ULN]; >3.0 – 10.0 x baseline if baseline is abnormal [>ULN]	>10.0 x ULN if baseline is normal [≤ULN]; >10.0 x baseline if baseline is abnormal [>ULN]
CPK (IU/l) - high	>ULN – 2.5 x ULN	>2.5 x ULN – 5 x ULN	>5 x ULN – 10 x ULN	> 10 x ULN
Haemoglobin (g/dl) increased	> ULN and increase from baseline]0 ;2] (g/dl)	> ULN and increase from baseline]2 ;4] (g/dl)	> ULN and increase from baseline > 4 (g/dl)	-
Haemoglobin (g/dl) - Anemia	[10;LLN[[8;10[< 8	-
White Blood Cells (g/l) - Low	[3.0;LLN[[2.0;3.0[[1.0;2.0[< 1.0

S 64315

CL1-64315-004 – Statistical Analysis Plan – Final V1.0

Parameter	Grade 1	Grade 2	Grade 3	Grade 4
Neutrophils (g/l) - Low	[1.5;LLN[[1.0;1.5[[0.5;1.0[<0.5
Lymphocytes (g/L) - Low	[0.8;LLN[[0.5;0.8[[0.2;0.5[<0.2
Platelets (g/L) - Low	[75;LLN[[50;75[[25;50[<25
aPTT (sec) - High	>ULN – 1.5 x ULN	>1.5 x ULN – 2.5 x ULN	>2.5 x ULN	-
ALT increased (IU/L)	>ULN – 3.0 x ULN if baseline is normal [\leq ULN]; 1.5 x baseline – 3.0 x baseline if baseline is abnormal [> ULN]	>3.0 x ULN – 5.0 x ULN if baseline is normal [\leq ULN]; >3.0 x baseline – 5.0 x baseline if baseline is abnormal [> ULN]	>5.0 x ULN – 20.0 x ULN if baseline is normal [\leq ULN]; >5.0 x baseline – 20.0 x baseline if baseline is abnormal [> ULN]	>20.0 x ULN if baseline is normal [\leq ULN]; >20.0 x baseline if baseline is abnormal [> ULN]
ALP increased (IU/L)	>ULN – 2.5 x ULN if baseline is normal [\leq ULN]; 2.0 x baseline – 2.5 x baseline if baseline is abnormal [> ULN]	>2.5 x ULN – 5.0 x ULN if baseline is normal [\leq ULN]; 2.5 x baseline – 5.0 x baseline if baseline is abnormal [> ULN]	>5.0 x ULN – 20.0 x ULN if baseline is normal [\leq ULN]; >5.0 x baseline – 20.0 x baseline if baseline is abnormal [> ULN]	>20.0 x ULN if baseline is normal [\leq ULN]; >20.0 x baseline if baseline is abnormal [> ULN]
AST increased (IU/L)	>ULN – 3.0 x ULN if baseline is normal [\leq ULN]; 1.5 x baseline – 3.0 x baseline if baseline is abnormal [> ULN]	>3.0 x ULN – 5.0 x ULN if baseline is normal [\leq ULN]; >3.0 x baseline – 5.0 x baseline if baseline is abnormal [> ULN]	>5.0 x ULN – 20.0 x ULN if baseline is normal [\leq ULN]; >5.0 x baseline – 20.0 x baseline if baseline is abnormal [> ULN]	>20.0 x ULN if baseline is normal [\leq ULN]; >20.0 x baseline if baseline is abnormal [> ULN]
GGT increased (IU/L)	>ULN – 2.5 x ULN if baseline is normal [\leq ULN]; 2.0 x baseline – 2.5 x baseline if baseline is abnormal [> ULN]	>2.5 x ULN – 5.0 x ULN if baseline is normal [\leq ULN]; >2.5 x baseline – 5.0 x baseline if baseline is abnormal [> ULN]	>5.0 x ULN – 20.0 x ULN if baseline is normal [\leq ULN]; >5.0 x baseline – 20.0 x baseline if baseline is abnormal [> ULN]	>20.0 x ULN if baseline is normal [\leq ULN]; >20.0 x baseline if baseline is abnormal [> ULN]

Any grade corresponds to a laboratory value with NCI-CTCAE version 5.0 grade 0, 1, 2, 3 or 4.

A grade 0 corresponds to a laboratory value within limit or reference range.

The LOWEST value for a patient is defined as the lowest absolute laboratory value during the treatment period.

A lowest value for a cycle is defined as the lowest laboratory value in that cycle.

The time to lowest value is defined from the date of the first IMP intake to the sampling date of the lowest value.

The time to lowest value in a cycle is defined from the first date of IMP intake in that cycle to the sampling date of the lowest value.

The HIGHEST value for a patient is defined as the highest laboratory value during the treatment period.

A highest value for a cycle is defined as the highest laboratory value in that cycle.

The time to highest value is defined from the date of the first IMP intake to the sampling date of the highest value.

Urinary results

The category positive includes results '+', '++', '+++', and '++++'.

The category negative corresponds to 'Absent' class.

Creatinine clearance

Creatinine clearance will be approximated by MDRD_GFR. This will be calculate as:

$\text{MDRD_GFR (mL/min/1.73m}^2\text{)} = 175 \times (\text{serum creatinine in mg/dL})^{-1.154} \times \text{age}^{-0.203} \times 0.742$ (if female) $\times 1.212$ (if black race).

Serum creatinine conversion:

$\text{Serum creatinine (mg/mL)} = \text{Serum creatinine (}\mu\text{mol/L)}/88.4$.

MDRD_GFR will be categorised in 4 categories:

- Normal renal function (MDRD_GFR >90 mL/min/1.73m²).
- Mild renal impairment (MDRD_GFR 60-90 mL/min/1.73m²).
- Moderate renal impairment (MDRD_GFR 30-59 mL/min/1.73m²).
- Severe (MDRD_GFR <30mL/mn/1.73m²).

Worst value

Worst value will be analysed as follow:

- For the urinalysis parameters, the worst class will correspond to 'Positive' class, then 'Trace' and finally 'Negative' will be considered as normal class.
- For creatinine clearance, the worst class will correspond to "severe" category, then "moderate", then "mild" and finally "normal".
- Baseline and post baseline worst grade for High and Low:
 - Low: If the result is below lower normal range limit, low =grade (for gradable parameter) or result (for non-gradable parameter), Else low=0.
 - High: If the result is above upper normal range limit, high =grade (for gradable parameter) or result (for non-gradable parameter), Else high =0.

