2.3.4. Expected overlapping toxicities

Based on preclinical data from both drugs, clinical data from azacitidine as a single agent in monotherapy as well as preliminary clinical data available from ongoing studies with S64315, bone marrow and lymphoid organs are identified as primary target organs for toxicity; overlapping myelosuppression may be observed. The risk of tumour lysis syndrome (TLS) has also to be considered. Other overlapping toxicities such as gastrointestinal disorders may be observed (see [section 8](#) for toxicity prophylaxis).

Even if pharmacology investigations indicate the potential for synergistic toxicity, no dedicated combination toxicity study had been considered since the safety of azacitidine is well known. The measures implemented, including clinical monitoring and described in the [section 8](#) of this document are deemed sufficient to mitigate the risk and to predict clinical dose adjustments.

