Creatine kinase (CK) / Creatine phosphokinase (CPK)	Grade ≥ 3 serum CK/CPK Grade 3 isolated electrolyte abnormalities (i.e. those occurring without clinical consequence) not recovered with or without intervention, to Grade < 2 level within 72 hours

TOXICITY	DLT CRITERIA
Electrolyte abnormalities (including magnesium, calcium, phosphorus, etc.) clinically significant	Any Grade 4 electrolyte abnormality
Cardiac disorders	QTcF interval \geq 501 ms or increase of $>$ 60 ms from baseline on at least two separate ECG assessments (1 assessment = triplicate ECG) Asymptomatic, absolute decrease in LVEF of 10% or greater from baseline AND LVEF $<$ 50% Asymptomatic, absolute decrease in LVEF of 20% or greater from baseline Troponin increase $>$ 10xULN or a troponin increase consistent with the diagnosis of a myocardial infarction (Grade 3) Symptomatic congestive heart failure
Skin and subcutaneous tissue disorders	Grade \geq 3 rash
Haematological abnormalities	Grade 4 neutropenia and/or thrombocytopenia persisting for 28 days after the start of azacitidine dosing in a cycle of therapy in the absence of active AML ($<$ 5% blasts) or active MDS or myelofibrosis
Other AEs	Any Grade \geq 3 AE Single event or multiple occurrences of the same event that lead to a dosing delay of $>$ 7 days in a cycle may be considered to be DLT by the Investigators and the Sponsor, even if not Grade \geq 3 Failure to restart test drug administration at the same dose due to drug-related toxicity Failure to restart test drug administration at the same dose within one cycle (i.e. 28 days) of the first missed dose due to delayed recovery from drug-related toxicity Failure to initiate cycle 1 after completing the LID period or failure to receive LID2 after receiving the LID1, due to drug-related toxicity
NCI CTCAE v5.0 will be used for grading	

The following criteria will not be considered as DLT:

- Grade 3 nausea, vomiting, diarrhoea, anorexia or constipation that do not result in hospitalization, tube-feeding or use of TPN
- Grade 3 fatigue, asthenia, fever
- Grade 3 isolated electrolyte abnormalities (i.e. those occurring without clinical consequence) that resolve, with or without intervention, to Grade $<$ 2 level in 72 hours

Patients who meet any of the criteria included in Table (4.1.3.5) 2 at the end of Cycle 1 will not be evaluable for DLT and therefore will be replaced during the dose escalation phase I part of the study, but not in the expansion parts of the study.

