10.6.2. PK/PD interpretation when applicable

Any potential PK/PD relationships with activity, efficacy and safety will be investigated through an exploratory analysis, and if relevant, a PK/PD Data Analysis Plan will be set up.

Description of analyses will be done in a separate PK/PD protocol.

PK/PD relationship will be assessed for clinical and biological efficacy endpoints including:

- Clinical response according to (Cheson, 2003)
- Biological response: bone marrow blast decrease
- Blood markers: WBC, neutrophils, platelets
- Any other clinically relevant endpoint

PK/PD relationship will be assessed for clinical and biological safety endpoints including:

- Cardiac events following narrow and broad definitions as in [section 8.2.5](#)
- Plasma troponin I and troponin T
- Left ventricular ejection fraction
- Neutrophil count
- Hepatic safety parameters (i.e. AST, ALT)
- Any other clinically relevant endpoint

Assessment of the PK/PD relationship for listed safety endpoints will be updated after each new cohort completion, when assessment of PK/PD relationship for efficacy will be performed at the end of dose escalation.

PK and relevant biomarker data may also be analysed in a Quantitative Systems Pharmacology analysis, which will be described in a separate protocol.

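### Discarding the whole white-cell differential when blasts are uncounted or the count is automated may understate the worst neutrophil and lymphocyte laboratory grades by an unknown amount, and the SAP plans no check on it.

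*SAP*

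**What the plan says.** SAP 4.2.3.4 starts from a general rule: "Only reliable values are considered for analyses. Unreliable values are flagged into the database". It then says of the differential, in which it names six cell classes with neutrophils and lymphocytes among them, that it "will be ignored if blast value is missing/not done or the differentiation is automated, as considered not reliable". Total WBC and platelets are not in the list of ignored values.

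Four other parts of the SAP decide what follows from this:

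- SAP 4.1.1 defines the worst post-baseline value as the worst among reliable values.
- SAP 3.4.4 lists low neutrophils and low lymphocytes as gradable and reports worst on-treatment grade against baseline grade.
- SAP Table (4.2) 4, row "Neutrophils (g/l) - Low", sets Grade 3 at 0.5 to below 1.0 and Grade 4 below 0.5. For total WBC, Grade 4 is below 1.0.
- SAP 3.1 shows no category for missing values unless the separate table shells ask for one.

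In the protocol, Table (8.2) 1 includes blasts in the haematology differential and does not say whether the count is manual or automated. Section 7.2 schedules blood films at baseline, C1D1 to C1D4, D1 of each later cycle and the withdrawal visit. Section 8.2.2 also asks for haematology with differential on D9, D16 and D23. Section 10.4.4.2 plans worst-grade shift tables and mentions no exclusion of this kind.

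**The concern.** The rule is triggered by the blast field or by the counting method, but it removes every cell class in the sample. Each removed sample is one that can no longer be the patient's worst. For a low count, that loss runs in one direction for the individual patient.

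Safety is the only objective this SAP addresses, and SAP 1.2 lists haematology with differential among the endpoints for it. Protocol 2.3.4 expects that "overlapping myelosuppression may be observed". The graded neutrophil table is the measurement-based view of that toxicity. If it rests on a selected subset of samples, the reader of the report needs to know how many were set aside and whether the result depends on them. As the SAP stands, neither would be visible.

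**Working it through.** The plan states no figure for this rule, so there is none to reproduce. The check follows the rule through the definitions, then asks what can be said about size.

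**1. From rule to table.** An ignored differential is not a reliable value (SAP 4.2.3.4). The worst value is the lowest reliable value (SAP 4.1.1), and it determines the worst grade (SAP 3.4.4). The minimum of a subset cannot be lower than the minimum of the full set. So, compared with the recorded data, a patient's worst low grade stays the same, becomes milder, or goes missing if no reliable value is left. The number of patients shown at Grade 4 can only fall. The percentage also depends on whether patients with no reliable value stay in the denominator, which the SAP text does not settle.

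**2. Which samples are exposed.** Comparing Protocol 7.2 with 8.2.2:

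| Draw | Haematology with differential | Blood film scheduled |
|---|---|---|
| C1D1, C1D2 | yes | yes |
| D1 of later cycles, withdrawal visit | yes | yes |
| D9, D16, D23 | yes | no |

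A missing manual count or blast value is therefore most plausible mid-cycle. This is an inference from the schedule. No passage says that mid-cycle differentials were automated or lacked blasts.

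**3. Size, under assumptions.** Let f be the share of differentials discarded and k the number of a patient's samples at his or her worst grade. The worst grade is lost if all k are discarded.

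- If discards are independent between samples, the probability of loss is f^k.
- If the method is fixed by the patient's laboratory, so that all of a patient's samples share one fate, the probability is f whatever k is.

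| f | k = 1 | k = 3, independent | k = 3, shared fate |
|---|---|---|---|
| 0.2 | 20% | 0.2³ = 0.8% | 20% |
| 0.5 | 50% | 0.5³ = 12.5% | 50% |
| 0.8 | 80% | 0.8³ = 51.2% | 80% |

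Neither f nor k is in the documents. The loss could be negligible or could affect most patients with that worst grade.

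**4. What is certain without a differential.** Neutrophils are part of the white-cell count, so neutrophils ≤ WBC. Applying the cut-offs in SAP Table (4.2) 4:

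- WBC < 0.5 G/L gives neutrophils < 0.5 G/L, which is Grade 4.
- WBC < 1.0 G/L (WBC Grade 4) gives neutrophils < 1.0 G/L, which is at least Grade 3.

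Total WBC remains in the analysis, so this information is available and unused. The bound is only a floor. A sample with WBC of 1.0 G/L or more can still have neutrophils below 0.5 G/L, and the bound would not show it.

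**The case against.** The exclusion is a reasoned choice. The SAP says it regards these differentials as unreliable. When blasts are uncounted or possibly misclassified, the other fractions may be wrong too. Putting every automated neutrophil count into the main table would override that judgement and bring in some misclassified values. This stands, and it is why the fix leaves the main rule in place.

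The protocol panel also asks for blasts, so a blank blast field is a departure from plan. All post-baseline values count, including re-tests and unplanned draws, so one lost sample need not change a patient's worst grade. Scheduled films on D1 of later cycles may still capture neutropenia that persists. These points limit the likely size but do not show that it is small. The table shells are not among the documents and may already carry a count of exclusions, but the SAP text does not call for one.

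A reader might go further and infer any of the following, which the documents do not support:

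- **That neutropenia at the nadir does drop out, or that the reported Grade 4 rate is the true rate times (1 − f).** The first needs discards to cluster at the nadir, which is nowhere stated. The second needs each patient to lose the worst grade with probability f, as with a single Grade 4 sample or a shared fate across samples.
- **That the DLT count is affected.** The protocol criterion is "Grade 4 neutropenia and/or thrombocytopenia persisting for 28 days after the start of azacitidine dosing in a cycle of therapy", but SAP 4.2.3.1 takes DLTs as the investigator reported them and does not recalculate them.
- **That severe neutropenia disappears from the report.** SAP 3.4.2 tabulates treatment-emergent adverse events by worst grade, independently of this rule, and total WBC and platelets remain graded. Under Protocol 8.2 a laboratory abnormality becomes an adverse event only if it has clinical impact or is judged medically important. The adverse-event tables therefore complement the laboratory table but do not replace it.
- **That response or PK/PD results are distorted.** Efficacy, PK and PD analyses lie outside this SAP (SAP 1 and 3.3).

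**Conclusion.** The point holds in a limited form. The rule removes neutrophils and lymphocytes along with blasts. Because worst grades use reliable values only, the worst on-treatment laboratory grades for those two parameters may be understated. The SAP has no count, fallback or sensitivity analysis to reveal this. The direction for an individual patient follows from the definitions; the amount is unknown and rests on f and k, which the documents do not give. Greater exposure of mid-cycle samples is plausible from the film schedule but not established. Only the differential-based laboratory tables are affected. The one part that needs no assumption is the bound from total WBC, which the plan leaves unused. This is a cheap improvement to a descriptive safety output and gives no reason to doubt the DLT or adverse-event results.

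**What to change.** Keep the reliability rule in SAP 4.2.3.4 for the main table and add three things:

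1. **A minimum grade.** Where a differential is excluded, assign the neutrophil grade that total WBC in the same sample implies: Grade 4 if WBC < 0.5 G/L, and at least Grade 3 (entered as Grade 3) if WBC is 0.5 to below 1.0 G/L. Flag patients whose worst grade rests on this derivation.
2. **A count.** Footnote the neutrophil and lymphocyte tables with the number of differentials excluded by dose level, and give the same count by visit so that any mid-cycle concentration can be seen.
3. **A sensitivity table.** Repeat worst neutrophil and lymphocyte grade with all recorded differentials kept, whatever the method or blast field.

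The cost is a short addition to the SAP, one derivation and one extra table, with no new data. The sensitivity table will contain some misclassified automated counts and should say so. The floor of Grade 3 can still be milder than the truth, so it does not replace that table.

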3.4.4. Clinical laboratory evaluation

Descriptive statistics on quantitative value and value by grade at baseline and worst grade on treatment according to the grade at baseline will be provided for gradable parameters (see [Table \(3.4.4\) 1](#)).

Table (3.4.4) 1 – Gradable parameters

Parameter		Worst Highest	Worst lowest	Gradable at baseline*
Blood biochemistry	Alanine aminotransferase (ALT)	High ALT	NA	No
	Albumin	NA	Low albumin	Yes
	Alkaline phosphatase (ALP)	High ALP	NA	No
	Amylase	High amylase	NA	Yes
	Aspartate aminotransferase (AST)	High AST	NA	No
	Bilirubin (total)	High total bilirubin	NA	No
	Cholesterol (total)	High cholesterol	NA	Yes
	Creatine phosphokinase (CPK)	High CPK	NA	Yes
	Gamma-glutamyl transferase (gamma-glutamyl transpeptidase) (GGT)	High GGT	NA	No
	Creatinine (serum)	High serum creatinine	NA	Yes
	Glucose	NA	Hypoglycemia	Yes
	Lypase	High lipase	NA	Yes
	Magnesium	Hypermagnesemia	Hypomagnesemia	Yes
	Potassium	Hyperkalemia	Hypokalemia	Yes
	Sodium	Hypernatremia	Hyponatremia	Yes
	Triglycerides	High triglycerides	NA	Yes
	Ionized calcium	High ionized calcium	Low ionized calcium	Yes
Blood haematology	Haemoglobin	High haemoglobin	Anemia	Yes for Low / No for High
	Lymphocytes	NA	Low lymphocytes	Yes
	Neutrophils	NA	Low neutrophils	Yes
	White blood cells (WBC)	NA	Low WBC	Yes

	Platelets	NA	Low platelets	Yes
Blood coagulation	Activated partial thromboplastin time (aPTT)	High aPTT	NA	Yes

Descriptive statistics on quantitative value and value by reference ranges at baseline and worst value on treatment according to baseline, with respect to the lower-limit normal (LLN) and the upper-limit normal (ULN) or by classes (<LLN / [LLN-ULN] / >ULN or normal / mild / moderate / severe for creatinine clearance) will be provided for non-gradable parameters (see [Table \(3.4.4\) 2](#)) and for parameters gradable post-baseline but non-gradable at baseline, in which case only baseline values will be presented.

Table (3.4.4) 2 – Non Gradable parameters

Parameter		Worst Highest	Worst lowest
Blood biochemistry	Bicarbonates	NA	Low bicarbonates
	Uric acid	High uric acid	NA
	Calcium (total)	Hypercalcemia	Hypocalcemia
	Creatinine clearance (approximated by the Modification of Diet in Renal Disease Glomerular Filtration Rate (MDRD GFR))	NA	Low creatinine clearance (Normal/mild/moderate/severe)
	Direct bilirubin	High direct bilirubin	NA
	High-density lipoprotein (HDL)	High HDL	NA
	Lactate dehydrogenase (LDH)	High LDH	NA
	Low-density lipoprotein (LDL)	High LDL	NA

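### SAP 4.2.3.4 stores 0 for any result of a non-gradable laboratory parameter that is not abnormal, so quantitative worst-value summaries built on that coding would give patients with no abnormality a laboratory value of 0

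*SAP*

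**What the plan says.** The rule is the last item under the worst-value heading of SAP 4.2.3.4. It is introduced as "Baseline and post baseline worst grade for High and Low", but its text covers non-gradable parameters by name:

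- Low direction: "Low: If the result is below lower normal range limit, low =grade (for gradable parameter) or result (for non-gradable parameter), Else low=0".
- High direction: "High: If the result is above upper normal range limit, high =grade (for gradable parameter) or result (for non-gradable parameter), Else high =0".

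The same section explains the zero for grades: "A grade 0 corresponds to a laboratory value within limit or reference range". It also lets all samples in: "Each post-baseline value (test, re-test, planned, unplanned) measured under treatment is taken into account for analyses".

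Two places define the extremes as observed results. SAP 4.2.3.4 states "The LOWEST value for a patient is defined as the lowest absolute laboratory value during the treatment period" and "The HIGHEST value for a patient is defined as the highest laboratory value during the treatment period". SAP 4.1.1 defines the worst post-baseline value as the worst reliable value on treatment, and defines lowest and highest likewise.

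For the non-gradable parameters of Table (3.4.4) 2, SAP 3.4.4 asks for "Descriptive statistics on quantitative value and value by reference ranges at baseline and worst value on treatment according to baseline". Both a numerical summary and a classification against LLN and ULN are therefore planned.

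**The concern.** On a grade scale, 0 is a genuine category and larger is worse. On a raw scale, 0 is a number below any positive result and stands for no sample that was taken. A rule that is sound for grades has been extended to raw results without changing the filler value.

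Table (3.4.4) 2 lists worst lows for bicarbonates, total calcium, phosphorus, haematocrit, red cells, basophils, free T3, free T4 and TSH. It lists worst highs for troponin I and T, CPK-MB, BNP, LDH, uric acid and others. Laboratory tests, TLS monitoring and cardiac markers are endpoints of the primary objective (SAP 1.2), and efficacy is not analysed (SAP 3.3), so safety tables are the core of the report. Two programmers could each follow a passage of the SAP faithfully and produce different means and medians. Because the rule also covers baseline, a normal baseline result would be stored as 0 as well.

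**Working it through.** The plan gives no figure to reproduce. The check applies the rule to short series and compares it with the observed-value definitions. All reference limits and laboratory values below are assumptions.

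**Coding.** For a non-gradable result x: low(x) = x if x < LLN, otherwise 0; high(x) = x if x > ULN, otherwise 0.

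**1. Patient with no abnormality.** Results 1.0, 1.1, 0.9; LLN 0.80, ULN 1.45.

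- Code first, then select: low = 0, 0, 0, so the worst low is 0. High = 0, 0, 0, so the worst high is 0.
- Select first, then code: the lowest is 0.9, not below 0.80, stored as 0. The highest is 1.1, not above 1.45, stored as 0.
- Observed-value definitions: 0.9 and 1.1.

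The zero appears in either order.

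**2. Patient with several low results.** Bicarbonates 24, 18, 12, 23; LLN 22. Coded low = 0, 18, 12, 0.

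| Order and operator | Worst low |
|---|---|
| Code each sample, take the minimum | 0 (a normal sample) |
| Code each sample, take the maximum, as for grades | 18 (the mildest low) |
| Select the worst observed value, then code | 12 |
| Observed-value definition | 12 |

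There are exceptions. If every result is low, the minimum of the coded values is right: 0.75, 0.6, 0.4 gives 0.4. If only one result is low, the maximum is right. In the high direction, a patient with any result above ULN gets the correct worst high by taking the maximum: 1.0, 1.8, 1.2 gives 1.8.

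**3. Effect on a group summary, high direction.** Five invented patients have highest BNP values of 40, 60, 80, 150 and 300; ULN 100.

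- Observed: (40 + 60 + 80 + 150 + 300)/5 = 630/5 = 126.
- Coded: (0 + 0 + 0 + 150 + 300)/5 = 450/5 = 90.
- Difference: (90 − 126)/126 = −29%. This holds in either order.

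**4. Effect on a group summary, low direction.** Simulated total calcium: mean 2.30, between- and within-patient SD 0.08, LLN 2.15, 12 samples per patient, 100,000 patients. Of these patients, 41% have at least one low value.

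- True mean lowest value: 2.17.
- Code first, minimum: 0 in 99.9% of patients; mean 0.002.
- Code first, maximum: mean 0.88. Of the patients with a low value, 59% get one less severe than their true lowest.
- Select first, then code: all of the 41% keep their true lowest value; the other 100 − 41 = 59% carry 0.

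A second simulation used other assumptions: 20,000 patients, 12 results each, mean 1.05, within-patient SD 0.2, between-patient SD 0.1 to 0.3, and the limits of step 1.

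- Mean worst low: 0.000 to 0.005 (minimum) or 0.44 to 0.51 (maximum), against a true value of about 0.72.
- Mean worst high: 0.47 to 0.68, against 1.37 to 1.38, with 60% to 70% of patients at 0.
- If the coded minimum were then classed against LLN, 100% of patients would fall below it, against 60% to 69% in truth.

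**5. Check on the remedy.** Ranges can differ within a patient: Protocol 8.2 allows inter-visit tests in local laboratories and updates to normal ranges. Take 2.12 with LLN 2.10 (normal) and 2.14 with LLN 2.15 (low). The observed minimum is 2.12, and classing only that sample gives within range. The low result at 2.14 is missed. Worst value and worst class therefore need separate derivations.

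**The case against.** The strongest reply is that the SAP never tells the programmer to take a minimum or maximum over coded values. It gives only a condition on the result. SAP 4.1.1 already defines the worst value, and the natural sequence may be to select it first and code it afterwards. Step 2 shows that this returns 12, the right answer. The sub-heading speaks of grade, so the coded variable may be meant only as an abnormality flag or for shift tables, with the quantitative summaries taken from the observed-value definitions. Which variable feeds which table is settled in the table shells, a separate document that is not available here.

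Much of this stands. A reader might infer that the reported worst low necessarily becomes 0 or the mildest low. The text does not support that, because it depends on an order and an operator that the SAP leaves open. Nor can it be said that the tables are certain to be wrong.

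A reader might also infer that patient management is affected, since a bicarbonate threshold appears in the protocol's azacitidine adjustment rules (Table (8.12) 2) and calcium and phosphorus belong to TLS monitoring. The documents do not support that either: those rules act on site results as they arise. DLTs are taken from the investigator's report and not recalculated (SAP 4.2.3.1), and escalation has already stopped (SAP 1.3.1).

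The reply does not remove the point. The rule names non-gradable parameters and stands under the worst-value heading, and no sentence limits it to a flag. Even in the most favourable order, a patient without an abnormality is stored as 0.

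**Conclusion.** The point holds in limited form. For non-gradable parameters, the SAP states a worst-value coding that conflicts with its own observed-value definitions. Used for the quantitative summaries of SAP 3.4.4, it assigns 0 to every patient without an abnormality in the given direction. Replacement of a true worst low by 0 or by the mildest low is possible, but only if samples are coded before selection.

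The size in this trial cannot be stated. It depends on which definition is programmed and on how many patients have no abnormality, and the documents give neither. The −29% for BNP, the 99.9% for calcium and the second simulation rest on invented inputs and illustrate direction only.

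The exposure is confined to descriptive safety tables for the parameters of Table (3.4.4) 2. Gradable parameters are unaffected because 0 is a valid grade. Urinalysis and creatinine clearance have their own class rules. No dosing or escalation decision rests on the coding. It should still be corrected before database lock, because the change is small and the tables include troponin, BNP and the TLS-related parameters.

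**What to change.** Amend the worst-value paragraph of SAP 4.2.3.4:

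1. Restrict the coding with 0 to gradable parameters.
2. For non-gradable parameters, set the quantitative worst low and worst high to the minimum and maximum reliable on-treatment result, citing the definitions already in SAP 4.1.1 and 4.2.3.4.
3. Derive the worst class separately. Compare every result with its own laboratory range (below LLN, within range, above ULN) and take the worst class in each direction, rather than classing only the extreme sample.
4. At baseline, use the observed baseline value and classify it against its own range.

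The cost is a few lines of SAP wording, a small programming change and a check that the table shells point to the right variables. No new data are needed.
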